8.6 UNANTICIPATED ADVERSE DEVICE EFFECTS

8.6.1 DEFINITION OF UNANTICIPATED ADVERSE DEVICE EFFECTS (UADES)

A UADE is any serious adverse effect on health or safety or any life-threatening problem or death caused by, or associated with, a device, if that effect, problem, or death was not previously identified in nature, severity, or degree of incidence in the investigational plan or application (including a supplementary plan or application), or any other unanticipated serious problem associated with a device that relates to the rights, safety, or welfare of subjects (21 CFR 812.3(s)).

The reporting of UADEs applies to non-exempt human subjects' research conducted or supported by HHS. Provide the definition of an UADE being used for this clinical trial. An incident, experience, or outcome that meets the definition of an UADE generally will warrant consideration of changes to the protocol or consent in order to protect the safety, welfare, or rights of participants or others. Other UADEs may warrant corrective actions at a specific study site. Examples of corrective actions or changes that might need to be considered in response to an UADE may include:

- Modification of inclusion or exclusion criteria to mitigate the newly identified risks
- Implementation of additional safety monitoring procedures
- Suspension of enrollment of new participants or halting of study procedures for enrolled participants
- Modification of informed consent documents to include a description of newly recognized risks
- Provision of additional information about newly recognized risks to previously enrolled participants.

8.6.2 UNANTICIPATED ADVERSE DEVICE EFFECT REPORTING

An investigator shall submit to the sponsor and to the reviewing Institutional Review Board (IRB) a report of any unanticipated adverse device effect occurring during an investigation as soon as possible, but in no event later than 10 days after the investigator first learns of the effect (21 CFR 812.150(a)(1)), a sponsor who conducts an evaluation of an unanticipated adverse device effect under 812.46(b) shall report the results of such evaluation to the Food and Drug Administration (FDA) and to all reviewing IRB's and participating investigators within 10 working days after the sponsor first receives notice of the effect. Thereafter the sponsor shall submit such additional reports concerning the effect as FDA requests (21 CFR 812.150(b)(1)).

8.6.3 REPORTING UNANTICIPATED PROBLEMS TO PARTICIPANTS

Notification of unanticipated adverse device effects (UADE) to study subjects will be managed and communicated by the PI.

9 STATISTICAL CONSIDERATIONS

9.1 STATISTICAL HYPOTHESES

A formal Statistical Analysis Plan (SAP) has been created, thus these sections will present summaries. Please refer to the SAP for additional detail. The study evaluates two primary endpoints: a 1-month endpoint and a 1-year endpoint. Both these endpoints blend safety and effectiveness measures so they are not termed “Safety Endpoint” or “Effectiveness Endpoint.”

Primary 1-Month Endpoint

The primary 1-month endpoint for the ChEVAS Cohort is defined as an event rate, including technical failure, and the occurrence of severe bowel ischemia, permanent paraplegia/paraparesis, renal failure, disabling stroke, abdominal aortic aneurysm rupture, and aneurysm-related mortality within 30 days of the index procedure. The null and alternative hypotheses are defined below.

$$H_0: \pi \geq 25\% \text{ vs. } H_1: \pi < 25\%$$

where π is the event rate at 30 days for the study test group, and 25% is the 30-day goal. A univariate test utilizing the exact binomial distribution will be performed to determine if the frequency of the 30-day

composite endpoint is statistically significantly less than the performance goal of 0.25. This is discussed further in the SAP.

Primary 1-Year Endpoint

The primary 1-year endpoint is defined as freedom from abdominal aortic aneurysm rupture and aneurysm-related mortality through 1 year (day 365), freedom from imaging-related findings in the 1-year window (Type or III endoleak, migration > 10 mm, AAA sac expansion > 5 mm, and occlusion within the ChEVAS System not seen at the index procedure), and open conversions and other major device-related interventions through day 365. The primary 1-year analysis will compare the treatment success composite to a target performance goal of 75%. The null and alternative hypotheses are defined below.

$$H_0: \pi \leq 0.75 \text{ vs. } H_1: \pi > 0.75$$

where π = the proportion of treated patients who meet the Treatment Success definition. A univariate test will be performed to determine if the frequency of subjects who meet the treatment success definition is statistically significantly higher than the performance goal of 0.75. This is discussed further in the SAP.

9.2 SAMPLE SIZE DETERMINATION

The number of patients enrolled into this study is driven by the performance goals, expected device performance, and requirements for the alpha error and power. Due to the decrease in number of evaluable subjects at 1 year, the size of the study is determined entirely by the 1-year primary endpoint. Given a minimum power requirement of 80%, alpha=0.05, target goal=75%, estimated 1-year performance of 85.7%, and the univariate binomial test plan, a minimum evaluable sample size of 103 is needed. Accounting for an approximate drop-out rate of 14%, 120 subjects would be needed to achieve the minimum power and alpha requirements. The 1-month endpoint assumes a target goal of 25%, estimated performance of 14.5%, and a similar univariate binomial test structure. Given that all 120 subjects will be analyzed for the primary 1-month endpoint, the 1-month endpoint has power of 85.6%. This is described further in the SAP.

9.3 POPULATIONS FOR ANALYSES

The Primary analysis will be conducted on the implanted population within the ChEVAS Roll-In and Pivotal cohorts. The Intention-to-Treat paradigm is not applied here as this is conventionally applied to two-armed randomized studies. Rather, all subjects receiving an implant are analyzed for the endpoint. The primary 1-year endpoint requires evaluable subjects, so completed cases (subjects who have enough information to be evaluated at 1 year) comprise an additional way to stratify the population. A subpopulation is the per-protocol population, consisting of subjects that have an implanted device, and have not violated the anatomical or procedural IFU criteria. Details of populations are explained further in the SAP.

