3 OBJECTIVES AND ENDPOINTS

3.1 1-MONTH PRIMARY ENDPOINT

The primary 1-month endpoint is defined in terms of an event rate, and includes technical failure and any of the following:

- *Severe Bowel Ischemia* – lack of adequate blood flow to the intestines leading to surgical/endovascular intervention or death and reported within 30 days of the index procedure
- *Permanent Paraplegia/Paraparesis* – event reported within 30 days of the index procedure without resolution at 30 days post-procedure
- *Renal Failure* – new onset renal failure requiring dialysis that remains on-going at 30 days post-procedure
- *Disabling Stroke* – new neurological deficit resulting from vascular insult reported within 30 days of the index procedure without resolution at 6 months post-procedure. Disabling is considered a value of 2 (slight disability) or above on the modified Rankin Scale (mRS) at both the 1-month and 6-month visits.
- *Abdominal Aortic Aneurysm Rupture* - Intraoperative and Post-procedural rupture through the aneurysm wall within the stented segment of the aorta reported within 30 days of the index procedure.
- *Aneurysm-related mortality* - death reported within 30 days of the index endovascular procedure

The technical success component of the endpoint (counterpart to technical failure) is defined as:

- a. Successful access and delivery of all ChEVAS components (i.e., ability to deliver each component to the intended location, without the need for unanticipated corrective intervention related to delivery);
- b. Successful and accurate deployment, defined as:
 - i. Deployment of the Nellix stent-grafts, Ovation limbs, and chimney(s) in the planned location;
 - ii. Patency of the Nellix stent-grafts, Ovation limbs, and chimney(s) with absence of device deformations (e.g., kinks¹, mal-deployment², misaligned deployment³) requiring unplanned placement of an additional device within the endovascular stent-grafts or chimney(s);
 - iii. Adequate seal without the need for unanticipated corrective interventions⁴. No use of components outside the defined ChEVAS System for the purpose of achieving seal. The use of adjunctive stenting for purposes outside of achieving seal or use

¹ Defined as a focal narrowing of the stent lumen of >50%, with concurrent stent wall deformation at that location.

² Defined as concluding the procedure without having all components of the ChEVAS System successfully deployed.

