³ Defined as, at the conclusion of the procedure, a > 10mm difference between the top of the Nellix stents, or the top of a visceral stent being > 14mm below the Nellix stent (the bag shelf is 4mm below the top of the Nellix stents).

⁴ Concomitant procedures, including those for infrequently encountered circumstances, may be anticipated and prepared for as part of a comprehensive endovascular approach

of adjunctive stents that are part of the defined system, does not result in technical failure.⁵

- c. Successful withdrawal (i.e., successful withdrawal of the delivery systems without the need for unanticipated corrective intervention related to withdrawal).

Multiple events occurring to a subject are considered a single subject failure for the purposes of calculating the composite one-month rate, as the rate is based on the total number of subjects. Since none of these variables are restricted by imaging requirements for detection, the cutoff date for the endpoint is exactly 30 days from the index procedure.

3.2 1-YEAR PRIMARY ENDPOINT

The primary 1-year endpoint is a blend of safety and effectiveness indicators. The endpoint is defined as the absence of:

- Abdominal aortic aneurysm rupture (0 - 365 days);
- Aneurysm-related mortality (0 – 365 days)
- Imaging-determined events at the 12-month imaging window. These do not require an intervention within 12 months to count as events:
 - Type I or Type III endoleak
 - Migration⁶ > 10mm
 - Sac Expansion⁷ > 5mm
 - Loss of Patency (100% occlusion) in Branches⁸, Nellix, or iliac limbs not seen at the index procedure
- Open conversion through day 365

⁵ Examples of acceptable procedures include:

- Placing an additional stent (Verta or Lifestent) to correct kink in visceral vessel (or a kink in the stent resulting from the vessel anatomy) or to smooth transition from Verta to visceral vessel (transition stenting)
- Placing an additional stent (Verta or Lifestent) to treat pre-existing visceral artery stenosis (spot stenting)
- Placing Verta stent within initial Verta stent due to length discrepancy, need to achieve a Verta length not covered by available lengths, or inadequate initial seal
- Placing Ovation limb to extend Nellix in order to obtain an adequate distal seal;
- Coiling of non-treated branch vessels
- Ballooning of any vessel or stent

⁶ As measured by the proximal end of the Nellix stents relative to the reference artery

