7 STUDY INTERVENTION DISCONTINUATION AND PARTICIPANT DISCONTINUATION/WITHDRAWAL

7.1 DISCONTINUATION OF STUDY INTERVENTION

If an attempt is made to insert one of the ChEVAS System catheters into the subject, the subject is considered enrolled. If the procedure is aborted subsequent to the attempted insertion, the case will be considered a technical failure. The subject will be exited from the study after having completed 30 days of follow-up and recording of all adverse events up until 30 days. A 30-day CT on such a subject is not required.

If a subject is Converted to Open Repair at any time during the study, the subject will be exited from the study after 30 days of follow-up post-surgery.

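### The 1-month primary test is limited to implanted subjects, so an enrolled case aborted with no implant is scored as a failure and then left out

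*Combined protocol and SAP*

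**What the plan says.** **Analysis population.** §9.3 says: "The Primary analysis will be conducted on the implanted population within the ChEVAS Roll-In and Pivotal cohorts". §4.1 repeats the sentence. §9.3 also sets intention-to-treat aside, as a convention for randomized two-arm studies, and adds that "all subjects receiving an implant are analyzed for the endpoint".

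**Enrolment and aborted cases.** §7.1 says: "If an attempt is made to insert one of the ChEVAS System catheters into the subject, the subject is considered enrolled". It continues: "If the procedure is aborted subsequent to the attempted insertion, the case will be considered a technical failure". Such a subject is followed for 30 days, with adverse events recorded, and then exits.

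**Endpoint.** §3.1 says: "The primary 1-month endpoint is defined in terms of an event rate, and includes technical failure and any of the following". The first requirement for technical success is "Successful access and delivery of all ChEVAS components". On counting, §3.1 says that several events in one subject are one failure, "as the rate is based on the total number of subjects".

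**Sample size.** §9.2 bases the 1-month power on everyone: "Given that all 120 subjects will be analyzed for the primary 1-month endpoint". The synopsis gives 120 as total enrolment, and §4.1 gives 120 as the sample size for the primary endpoints.

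§9.1 and §9.3 refer to a separate SAP for detail. Its text was not part of what was reviewed.

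**The concern.** The two rules disagree about one kind of subject: enrolled, procedure aborted, nothing implanted. §7.1 and §3.1 make that subject a 1-month failure. §4.1 and §9.3 remove the same subject from the analysis. A case aborted after a partial implant presumably stays in and fails, so the most complete technical failure is the one that disappears. No reviewed section brings these subjects back.

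The 1-month endpoint is a single-arm exact test against a fixed 25% event rate, so there is no control arm in which the same exclusion could offset itself. Each excluded subject is an event by definition, which means the exclusion can only lower the observed rate. Leaving the conflict open would also allow the denominator to be chosen after the counts are known.

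**Working it through.** **Inputs.** Goal 25% (§9.1). Expected event rate 14.5%, alpha 0.05, N = 120 and stated power 85.6% (§9.2). Exact binomial test (§9.1). The number of sides is not stated; one-sided 0.05 is used because it reproduces the stated power.

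**1. The plan's own figure.** The largest c with P(X ≤ c | 120, 0.25) ≤ 0.05 is c = 21, where the probability is 0.0330. Power is P(X ≤ 21 | 120, 0.145) = 0.8556, the stated 85.6%. One-sided 0.025 gives c = 20 and power 0.7925, which does not match. The stated power therefore rests on 120 analysed subjects.

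**2. One no-implant case among 120 enrolled.** The cut-off stays at 21 for n = 117 to 120.
- Implanted only: P(X ≤ 21 | 119, 0.25) = 0.0367, pass.
- All enrolled: 21 + 1 = 22 events, P(X ≤ 22 | 120, 0.25) = 0.0534, fail.

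**3. Range for the no-implant rate q.** The documents give none. §2.3.4.1 reports 100% technical success in the cited series, and §2.4.2 puts them at more than 200 patients. For 0/200 the one-sided 95% upper bound is 1 − 0.05^(1/200) = 0.0149, so q is taken as 0 to 1.5%. This is an assumption.

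**4. False-pass chance, implanted-only, when the all-enrolled event rate is 25%.** Let K ~ Bin(120, q) be the number of no-implant cases. The remaining 120 − K have event probability (0.25 − q)/(1 − q) and are tested at the cut-off for their own n. Counting all enrolled gives 3.3% at every q.

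**5. Chance that the choice of population alone decides the verdict.** Sum over k of P(K = k) × [P(X ≤ cut(120 − k)) − P(X ≤ 21 − k)], with X ~ Bin(120 − k, p). Two readings of 14.5% are shown: as the rate among implanted subjects (p = 0.145), and as the rate among all enrolled (p = (0.145 − q)/(1 − q)).

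**6. Power on all enrolled if 14.5% is the implanted-only rate.** P(X ≤ 21 | 120, q + (1 − q) × 0.145).

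| q | P(K = 0) | False pass (step 4) | Verdict decided, 14.5% implanted | Verdict decided, 14.5% enrolled | Power (step 6) |
|---|---|---|---|---|---|
| 0 | 100% | 3.3% | 0 | 0 | 85.6% |
| 0.25% | 74% | 3.8% | 1.9% | 1.8% | 84.0% |
| 0.5% | 55% | 4.3% | 3.8% | 3.4% | 82.2% |
| 1% | 30% | 5.5% | 7.9% | 6.1% | 78.5% |
| 1.5% | 16% | 6.8% | 12.1% | 8.2% | 74.5% |

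The false-pass chance reaches 5% at q of about 0.8%, roughly one subject in 120 (0.008 × 120 = 0.96). Power in the last column falls below 80% at about the same q.

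**The case against.** **The SAP may resolve it.** §9.3 sends population details to the SAP and §9.4.2 sends endpoint methods there, and the protocol does not define the implanted population further. This stands as a limit: it cannot be shown that the final analysis will drop these failures. It does not remove the conflict, because whichever reading the SAP takes, part of the protocol needs correcting.

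**§9.2 could be read as the specific rule for 1 month.** All 120 subjects are to be analysed, and the only subjects §4.1 expressly removes from every analysis are those who withdraw before the procedure. This is a fair reading of intent, but §9.3 explicitly replaces intention-to-treat with a rule based on receiving an implant. The phrase in §3.1 about the total number of subjects is weak support either way, since its purpose is to count multiple events once.

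**The false-pass figures depend on the estimand.** If 25% is the event rate among implanted subjects, the implanted-only test stays at 3.3% to 3.8% over the same range. That is correct. It means the written test is valid for a narrower question, one that omits failures the endpoint definition includes.

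**Replacement is not ruled out.** §7.2 bars replacement only for subjects who received the intervention. If no-implant cases were replaced to reach 120 implanted, one case would not flip the result at the cut-off (22/121, p = 0.048), but two would (23/122, p = 0.069, against 21/120, p = 0.033). The direction of the bias is unchanged.

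**The upper end of the range is a confidence bound.** The cited series report no technical failures, so the effect may well be zero. This stands.

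**Conclusion.** The concern holds. As written, §4.1 and §9.3 exclude from the 1-month test subjects whom §7.1 and §3.1 declare to be 1-month failures, and the exclusion can only help the device.

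The size depends on an abort rate that the documents do not give. With no aborted, no-implant case there is no effect. With one among 120 enrolled, a result at the cut-off changes from fail to pass. Over the assumed range up to 1.5%, the population choice alone decides the verdict with a chance of up to 12.1% if 14.5% describes implanted subjects, or 8.2% if it describes all enrolled. All figures assume a one-sided exact test at 0.05; those in the table also assume 120 enrolled without replacement.

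This should be corrected before the results are known, because it concerns the denominator of a primary endpoint.

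**What to change.** 1. In §4.1 and §9.3, and in the SAP if it says the same, define the primary 1-month population as all enrolled ChEVAS Roll-In and Pivotal subjects. Count cases aborted after attempted insertion as failures, as §7.1 already does. Report the implanted set as a supportive analysis.
2. Use one enrolment trigger throughout. §1.2 and §7.1 use an attempt to insert any ChEVAS System catheter; §4.1 and §5.3 require that a catheter is inserted; §8.3 names only the Nellix catheter. Adopt attempted insertion of any system catheter, as in §7.1. Otherwise a complete access failure could fall outside even an all-enrolled set.
3. In §9.2, state that the 14.5% covers all enrolled subjects, or restate the power. Say whether no-implant cases may be replaced.

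The cost is mostly wording. Aborted cases are already followed to day 30, so no new data are needed, and §9.2 sizes the trial on the 1-year endpoint. The observed 1-month rate may look slightly less favourable. If 14.5% applies only to implanted subjects, 1-month power falls from 85.6% to 82.2%, 78.5% and 74.5% at 0.5%, 1% and 1.5% aborted.

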9.4 STATISTICAL ANALYSES

9.4.1 GENERAL APPROACH

Page 63 of 82

Confidential. The data and information contained herein is proprietary and confidential and may not be used, disclosed, or reproduced with prior written permission from Endologix, Inc.

Analysis depends on the variable type. For nominal variables, summary statistics will include counts and proportions. Exact confidence limits for binomial variables will be given when they aid in understanding the results. Comparisons will be made with Fisher's Exact Test for 2x2 tables, and the extension of the test (Fisher-Freeman-Halton) when more than 2 categories exist. For continuous variables, summary statistics will be presented including means (or medians for non-normal distributions), standard deviations (or quartile estimates for non-normal distributions), and range. Quantitative comparisons of demographics and vascular variables between sites will be performed by 2-sided F-tests. Unless otherwise specified, the exact form of each algorithm will be the default of SAS version 9.4 or later (SAS Institute, Cary, NC).

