Description of Study Intervention:	The ChEVAS System consists of the Nellix® System (to treat juxtarenal, pararenal, and/or paravisceral aneurysms) used in conjunction with the Verita™ Self-Expanding Branch Stent Graft System (to maintain renal/visceral blood flow) and Ovation® iX iliac limbs/extensions, if needed (to ensure adequate distal seal zone). The ChEVAS System is intended to provide a sealing zone from the proximal extent of the device (healthy aortic neck) throughout the aneurysm and to the distal aspect of the device implanted into the iliac arteries. The proximal end of target landing zone is below the celiac for SMA and bilateral renal artery chimneys, below the SMA for bilateral renal artery chimneys, and below the proximal renal artery for distal renal artery chimney.
Study Duration:	The study enrollment is projected to last from 18 to 24 months, with a primary endpoint at 1 year of follow-up. The total follow-up requirement will be 5 years. Therefore, the primary endpoint will be ready for analysis roughly 30 to 36 months after trial initiation, with the final subject exiting the trial 96 months after enrollment began.
Participant Duration:	Subjects will be followed procedurally to discharge, at 30 days, six months, one year and annually thereafter to five years (total follow-up commitment).

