The PERICLES Registry treated 517 high-risk patients with paravisceral AAAs between 2008 and 2014.⁶² There were 119 patients treated at 2 U.S. centers and 398 patients treated at 3 European centers. A total of 898 chimney grafts were implanted in conjunction with a variety of commercially available endografts. Of the total 898 chimney grafts, 692 were renal chimneys, 156 were SMA chimneys, and 50 were celiac chimneys. Of these, 49.2% (442 stents) were balloon-expandable covered stents (Advanta V12/iCAST) and 39.6% (355 stents) were self-expanding covered stents (Viabahn). Balloon-expandable bare-metal stents were used as the primary chimney stent in 11.2% of the cases. Bare-metal Nitinol stents were used to reline the inside of a covered chimney stent in 25.4% (220/898) of the cases. Twenty-five post-operative deaths (4.9%) occurred within 30 days for the entire cohort, but 18 (3.7%) post-operative deaths occurred within 30 days in elective patients. Nine (9) patients (1.7%) had an embolic stroke. At a mean follow-up of 17 months, primary patency was 94%, secondary patency of 95%, 7.9% presented with Type Ia endoleak, and 6.6% required a secondary intervention. Survival was 85% at 1-year follow-up and 77% at 2 years.

The PROTAGORAS study treated 128 high-risk patients with pararenal AAAs at 2 European centers.⁶³ A total of 187 chimney grafts were implanted in conjunction with the Endurant endograft. All procedures were completed successfully. One post-operative death occurred within 30 days (0.8%) due to cardiac decompensation. Two patients (1.6%) presented with new onset of Type Ia endoleak. Primary chimney graft patency was 95.7%. Eight (8) chimney grafts were occluded during follow-up. Six (6) patients required intervention to resolve renal artery stenosis. Freedom from chimney graft-related reinterventions was 93.1%. Over 17 months mean follow-up, survival was 83%.

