3.3.4 OUTCOMES

Additional outcomes will be collected for each follow-up time point through 5 years post procedure. All outcomes will be differentiated, where appropriate, by the stents involved (Nellix vs. Verta stents)

- Mortality (all-cause and aneurysm-related)
- MAE Individual Components
- Aneurysm Rupture
- Conversion to Open Repair
- Adverse Events
- Renal Function (assessed via creatinine and eGFR)
- All Types of Endoleak (Ia, Ib, Ic, II, III, IV, or unknown)

- Gutters
- Device Patency and Integrity
 - Stenosis
 - Occlusion
 - Kinking
 - Fracture
- Aneurysm Sac Diameter
- Migration (e.g., migration > 5 mm, migration > 10 mm, clinically significant migration)
- Secondary Procedures
 - All Types of Endoleaks
 - Device stenosis/occlusion
 - Device kink
 - Device fracture
 - Luminal thrombus
 - Rupture
 - Migration
 - Aneurysm sac expansion
 - Device defect
 - Gutters

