9.4.4 SAFETY ANALYSES

As mentioned, prior, there is no specific endpoint dedicated solely to safety. Both primary endpoints will be evaluated, and each contains information regarding safety. Additional analyses regarding major adverse events will be presented in a descriptive fashion. Adverse events will be tabulated per their system organ class and presented descriptively. Please refer to the SAP for additional details.

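### No time-to-event estimator, denominator or censoring rule is stated for the clinical events followed to 5 years; the only stated summary, counts and proportions, is biased once subjects are lost to follow-up

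*Combined protocol and SAP*

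**What the plan says.** Synopsis 1.1 sets the horizon: "The total follow-up requirement will be 5 years". Section 3.3.4 says "Additional outcomes will be collected for each follow-up time point through 5 years post procedure", and its list includes all-cause and aneurysm-related mortality, MAE components, rupture, conversion and secondary procedures. It names no estimator.

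Section 9.4.1 gives the general rule: "For nominal variables, summary statistics will include counts and proportions". It adds that "Exact confidence limits for binomial variables will be given when they aid in understanding the results". Section 9.4.4 says of safety: "Additional analyses regarding major adverse events will be presented in a descriptive fashion". Section 9.4.3 plans no formal secondary tests and adds only a year-2 exact one-sided interval for migration and sac enlargement.

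Section 9.3 names implanted subjects and, for the 1-year endpoint, completed cases. It gives no denominator for years 2 to 5. Section 7.1 ends follow-up 30 days after an open conversion. Section 9.1 says that section 9 summarises a separate SAP, and several subsections, 9.4.4 among them, refer to it for detail.

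**The concern.** These are dated events, and the subjects at risk leave over time through death, withdrawal, loss to follow-up and exit after conversion. A binomial proportion needs each subject's status at year t. Once some statuses are unknown, a proportion over everyone enrolled counts lost subjects as event-free, while a proportion over those still attending removes the subjects who died. Neither estimates the risk of the event by year t, and the two err in opposite directions. With no denominator fixed in advance, the choice could be made after the data are seen.

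The long-term rates carry weight here. Both primary endpoints close at about 1 year, while the protocol's background (2.3.4.1 and 2.4.1) places this platform's migration, sac enlargement and graft failure largely after the first year. Later re-intervention, conversion, rupture and death show whether those findings have clinical consequences.

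**Working it through.** **The plan's own figures.** The plan gives no 5-year event rate to reproduce. Its design figures do reproduce. For the 1-year endpoint section 9.2 says "a minimum evaluable sample size of 103 is needed". An exact binomial test at one-sided 0.05, with 75% against 85.7%, gives n = 103, success at 85 or more, actual alpha 0.0456 and power 85.5%. Power is 79.8% at n = 102 and stays at or above 80% from 103 on. Allowing for 14% drop-out, 103/0.86 = 119.8, so 120. The 1-month power at n = 120 is 85.56%, against 85.6% stated. None of this depends on how 5-year outcomes are summarised.

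**Inputs for the illustration**
- Mortality: the chimney EVAR registry in section 2.3.3.1, "Survival was 85% at 1-year follow-up and 77% at 2 years". Hazard in year 1: d1 = −ln(0.85) = 0.1625. Hazard in year 2: d2 = −ln(0.77/0.85) = 0.0988, assumed to continue to year 5.
- Loss or withdrawal: hazard l = 0.03, 0.05 or 0.08 a year, independent of outcome (assumption). Without deaths this is 1 − exp(−5l) = 14% to 33% lost by year 5.
- Re-intervention: hazard r = 0.08 a year (assumption).

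**Formulas.** For an event with hazard h, and total hazards a1 and a2 of everything that ends observation or the event-free state in year 1 and in years 2 to 5, the expected proportion with the event is

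P = (h1/a1)(1 − exp(−a1)) + exp(−a1)(h2/a2)(1 − exp(−4·a2)).

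- True mortality: 1 − exp(−d1 − 4·d2) = 1 − 0.572 = 42.8%.
- Deaths over all enrolled: h = d, a = d + l.
- True cumulative incidence of re-intervention: h = r, a = r + d.
- Re-interventions over all enrolled: h = r, a = r + d + l.
- Ever re-intervened, among those still attending at year 5: 1 − exp(−5r).

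**Numbers put in at l = 0.05**
- Deaths over all enrolled: (0.1625/0.2125)(0.1914) + 0.8086(0.0988/0.1488)(0.4486) = 0.146 + 0.241 = 38.7%.
- True re-intervention: (0.08/0.2425)(0.2153) + 0.7847(0.08/0.1788)(0.5110) = 0.071 + 0.179 = 25.0%.
- Re-interventions over all enrolled: (0.08/0.2925)(0.2536) + 0.7464(0.08/0.2288)(0.5996) = 0.069 + 0.157 = 22.6%.
- Among year-5 attendees: 1 − exp(−0.4) = 33.0%.

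| Annual loss | Death, true | Death, all enrolled | Re-intervention, true | Re-intervention, all enrolled | Re-intervention, attendees |
|---|---|---|---|---|---|
| 0 | 42.8% | 42.8% | 25.0% | 25.0% | 33.0% |
| 3% | 42.8% | 40.3% | 25.0% | 23.5% | 33.0% |
| 5% | 42.8% | 38.7% | 25.0% | 22.6% | 33.0% |
| 8% | 42.8% | 36.6% | 25.0% | 21.3% | 33.0% |

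The zero-loss row shows that deaths alone leave the all-enrolled proportion unbiased. With loss, it understates death by 2.5 to 6.2 points and re-intervention by 1.5 to 3.8 points. The attendee proportion overstates re-intervention by 33.0 − 25.0, about 8 points, at any loss rate.

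**Sensitivity.** Take constant hazards with 40% dead by year 5 and 30% re-intervened if death did not intervene. The true values are then 40.0% and 23.8%. With 14%, 30% and 50% lost by year 5, the all-enrolled proportions are 37.4%, 34.2% and 29.7% for death, and 22.4%, 20.6% and 18.1% for re-intervention. The direction is the same and the gap widens with loss.

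**Choice of estimator.** Kaplan-Meier with deaths censored targets 1 − exp(−5r) = 33.0% for re-intervention, the same overstatement as the attendee proportion. It suits all-cause death; the other events need cumulative incidence.

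**The case against.** The strongest objection is that the gap is shown only for the supplied text. Section 9 calls itself a summary, and 9.4.1 is a general, non-exclusive rule that names no outcome or time point. A reader might infer that the sponsor has committed to crude proportions for the 5-year events. The documents do not support that, because the SAP may already specify time-to-event methods. This stands, and it makes the request conditional on what the SAP says.

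Second, size. At 5% annual loss the all-enrolled bias is about 4.0 points for death (42.8 − 38.7, before rounding) and 2.5 for re-intervention. With 120 subjects the standard errors are √(0.428 × 0.572/120) = 4.5 points and √(0.25 × 0.75/120) = 4.0 points, so the bias is below one standard error. The 8-point error needs an attendee denominator that no section specifies. Both facts stand. But the bias has a known direction and is avoidable at almost no cost.

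Third, the inputs. The registry enrolled high-risk patients treated with other endografts, while section 5.2 excludes a life expectancy under 2 years. The protocol forecasts no 5-year mortality, and section 9.2 does not say whether its 14% includes deaths. The figures are therefore illustrative.

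Fourth, migration and sac enlargement, the late failures most discussed in the background, already have a year-2 interval in 9.4.3. That is correct, but it does not cover the dated clinical events.

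**Conclusion.** The point holds in limited form. For events followed to 5 years, the supplied text states no time-to-event estimator, denominator or censoring rule, and its only stated summary for categorical outcomes is biased under loss to follow-up. On registry-based mortality, 3% to 8% independent annual loss and an 8% annual re-intervention hazard, an all-enrolled proportion understates 5-year death by about 2 to 6 points and re-intervention by about 1.5 to 4 points. An attendee-only re-intervention proportion would overstate by about 8 points. The loss and re-intervention rates, and the extension of mortality beyond year 2, are assumptions.

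Two stronger readings are tempting and do not hold. A reader might infer that high mortality by itself invalidates proportions; with everyone enrolled in the denominator and no loss, it does not. A reader might also infer that survival methods would recover the right rates from the same data. They assume independent censoring, and exit 30 days after open conversion (7.1) depends on the outcome: deaths after that exit are not collected, and no estimator recovers them.

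Only descriptive long-term results are affected. The primary tests, the sample size and the power stand.

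**What to change.** In 9.4.1 and 9.4.4, and in the SAP unless it already says so, state:

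- All-cause mortality is estimated by Kaplan-Meier.
- Aneurysm-related death, rupture, open conversion, secondary procedures and the MAE components other than all-cause death are estimated by cumulative incidence (Aalen-Johansen), with other death as a competing event.
- Each estimate is given with a 95% confidence interval and the number at risk at each visit time (30 days, 6 months, years 1 to 5).
- The starting population and the censoring rule are named. Counts are kept as supporting tables.
- These estimates assume independent censoring, and exit 30 days after open conversion limits the mortality estimate.

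The cost is a few lines of text and standard SAS procedures applied to event, death and exit dates that the study needs in any case. No sample size, test or performance goal changes.
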